## **Background and Introduction**

---

### **Study Background and Information:**

Cochlear Implants are now a well-accepted treatment for severe to profound hearing impairment. Bilateral cochlear implants are known to provide access to some of the benefits of binaural hearing like improved speech understanding in noise (primarily due to headshadow), improved localization, reduced stress and fatigue, and improved quality of life (e.g., Dunn et al. 2012, Litovsky et al. 2012, Härkönen et al. 2016, Reeder et al. 2014, Agrawal 2008). However, a number of CI recipients are unable to or choose not to be implanted bilaterally for many reasons. Those with acoustic hearing in the contralateral ear can benefit significantly by using a hearing aid in that ear (bimodal hearing) (Ching et al. 2006, Dorman and Gifford 2010, Dorman et al. 2015, Dunn et al. 2005, Firszt et al. 2012, Illg et al. 2014, Farinetti et al. 2015).

Unilateral CI recipients do not have access to advantages of bilateral and bimodal hearing. In addition to reduced speech understanding in noise, especially when the speech source is located towards the non-CI, they can also experience increased stress and fatigue.

### **About the Naida Link CROS:**

The Naida Link CROS device extends the Naida family of hearing solutions from AB and Phonak for severe-to-profound individuals. Utilizing the proprietary Binaural VoiceStream Technology, an automatic wireless network is established between the Naida CI sound processor and a Naida Link CROS transmitter, Naida Link hearing aid, or second Naida CI sound processor. This wireless network enables the sharing of control signals, and full-bandwidth audio streaming so that all cochlear implant recipients can benefit from hearing from both ears. The Naida Link CROS allows unilateral cochlear implant recipients to hear from wherever they want and walk into any listening situation with more confidence.

Phonak Naída Link CROS device + AB Naída CI sound processor = Naída Link CROS solution

## **Purpose and Objectives**

---

### **Purpose and Objectives:**

The purpose of this study is to assess the effect of the Naida Link CROS device on speech understanding in challenging listening situations and on the quality of life in unilateral CI recipients and their frequent communication partners. We hypothesize that:

- (a) Unilateral CI recipients will obtain higher speech understanding scores with the CROS device in challenging listening conditions

(b) Use of the CROS device will lead to positive changes in ratings on Quality of Life measures for (i) unilateral CI recipients, and (ii) their frequent communication partners

A frequent communication partner (FCP) is an individual (a family member, or a friend, or a care taker, or a significant other, or a colleague, etc.) who has at least two hours of in-person interactions with the CI recipient every week.

## **Study Population**

---

**Age of Participants:** 18+

**Sample Size:**

At Utah: 15  
All Centers: up to 35

**Inclusion Criteria:**

**Study participants' inclusion criteria:**

- i. Unilateral recipients of Advanced Bionics CII/90K/Ultra implants
- ii. Ages 18 years and above
- iii. At least 6 months of CI use experience
- iv. Current users of a Naida CI Q70 or Q90 processor
- v. Do not currently use a Naida Link CROS device
- vi. Limited usable/aidable hearing in the contralateral ear
- vii. Fluent in spoken English
- viii. Willingness to use the CROS device regularly for the study duration
- ix. Willingness to follow-up on a biweekly/monthly basis

**FCP's participants' inclusion criteria:**

- i. A FCP of a recipient of a unilateral Advanced Bionics CII/90K/Ultra implants
- ii. Ages 18 years and above
- iii. Fluent in spoken English
- iv. Willingness to participate in the study

**Exclusion Criteria:**

**Exclusion criteria:**

- i. < 6 months of CI use experience
- ii. < 30% sentence recognition scores in quiet with unilateral CI
- iii. Inability to participate in speech testing
- iv. Inability to follow and complete questionnaires
- v. Inability to designate an FCP

## **FCP's Exclusion criteria:**

- i. Not a FCP of a recipient of a unilateral Advanced Bionics CII/90K/Ultra implants
- ii. Under the age of 18 years
- iii. Not fluent in spoken English

## **Design**

---

Survey/Questionnaire Research  
Prospective Clinical Research

## **Study Procedures**

---

### **Recruitment/Participant Identification Process:**

Participants will be identified by [name], [name], [name].

They will be able to identify current patients that have received the Advanced Bionics implant and have had it for at least 6 months.

Potential participants will be approached in clinic to provide informed consent.

### **Informed Consent:**

#### **Description of location(s) where consent will be obtained:**

Consents will be obtained in the ENT clinic at the University of Utah.

#### **Description of the consent process(es), including the timing of consent:**

For the Cochlear Implant Patient: A study team member will provide the patient with an information form on the study design that should be read to and/or discussed with the patient in an understandable way. In this document, patients willing to consent to participate in this study will be informed of the nature, extent, design and conduct of the study and their consent will be obtained in writing prior to inclusion to the study schedule. Patients will be given the opportunity to ask questions and will be informed of their right to withdraw from the study at any time, for any reason. For the Communication Partner: A study team member will provide the communication partner with an information form on the study design that should be read to and/or discussed with the partner in an understandable way. In this document, communication partners are informed about the nature and extent of their participation in the study. Their consent will be obtained in writing prior to inclusion to the study schedule. Communication partners will be given the opportunity to ask questions and will be informed of their right to withdraw from the study at any time, for any reason. Communication partners will be informed that they are not required to participate even if the Cochlear implant patient wishes to enroll. The study team will ensure that the participants know that enrollment in the study is voluntary.

**Procedures:****Screening:**

The PI will refer eligible patients to the study team. Someone from the team will present the study to the patient for recruitment. After recruiting, following will be mailed to the participants to be completed prior to the study visit and hand carried to visit 1:

For each CI subject:

- i. Informed consent form
- ii. APS-SSD (Schafer et al, 2013, modified by H. Snapp, 2017)
- iii. Nijmegen questionnaire (adapted from Hinderink et al, 2000)

For each CI subject's frequent communication partner:

- i. Informed consent form
- ii. SOS-HEAR

**Following are the procedures for visit 1 (Estimated total duration of 2 hours):**

- a. Review and sign consent forms and the pre-intervention questionnaires for CI subjects and their FCPs (15 minutes)
- b. Collect demographic information (15 minutes)
- c. Conduct unaided pure-tone audiometry using insert earphones for each ear (15 minutes)
- d. Connect CI participant's own Naida CI processor to SoundWave to obtain the following pre-intervention data-logged information (5 minutes):
  - i. Duration of daily CI use
  - ii. The proportion of time spent in noisy environments (by level)
- e. Program the study CI processor (5 minutes):
  - i. Initialize the processor to communicate with CROS
  - ii. Create a study program using recipients' everyday program as a baseline:
    - i. Use omnidirectional mic mode
    - ii. 100% T-Mic
    - iii. If ClearVoice is OFF in baseline program, activate it and set it to medium in the study program. Increase M-levels globally, based on recipient's feedback.
- f. Measure benefit in speech understanding with CI only and with CI+CROS in the following listening configurations (50 minutes)
  - i. SpeechFront
  - ii. SpeechCROS(Off)
  - iii. SpeechCROS(Off)NoiseCI
  - iv. SpeechCROS(On)NoiseCI
- g. Program recipients' own Naida CI processor for the take-home phase (5 minutes):
  - i. Program 1 would be the same as the CI recipient's preferred everyday program but with CROS activated

- ii. Program 2: noise program with CROS enabled:
  - i. UltraZoom (if own processor is a Naida CI Q70)
  - ii. StereoZoom (if own Q90)
- h. Provide instructions for chronic use of the new CI programs and CROS (10 minutes)

**Following are the procedures for visit 2 (Estimated total duration of 1 hour):**

- a. Obtain post-intervention questionnaire ratings from CI recipients (complete on the same forms that were used for pre-intervention ratings) (30 minutes)
  - i. APS-SSD (Schafer et al., 2013, modified by H. Snapp, 2017)
  - ii. Nijmegen questionnaire (adapted from Hinderink et al., 2000)
- b. Obtain post-intervention questionnaire ratings from FCPs (complete on the same form that was used for pre-intervention ratings) (to be completed while the CI recipients are working on their questionnaires)
  - i. SOS-HEAR
- c. Connect participant's own Naida CI processor to SoundWave to obtain the following post-intervention data-logged information: (conducted while participants are completing questionnaires)
  - i. Duration of daily CI use
  - ii. The proportion of time spent in noisy environments (by level)
- d. Program the study Naida CI Q90 for sound booth testing: (conducted while participants are completing questionnaires)
  - i. Program 1: Same as that used for speech testing in visit 1
  - ii. Program 2: Same as P1 but with UltraZoom ON.
- e. Measure benefit in speech understanding with CROS device at the same SNR that was used in visit 1 (15 minutes)
  - i. SCROS(On)NCI (with P1, to assess the effect of chronic experience)
  - ii. SFrontNBack (with P1 and with P2, to assess the benefit of UltraZoom)
- f. Review study findings. The recipients can choose if they want to keep the CROS device for everyday use at this point. They would be advised that they would be responsible for any extended warranty needs. Program settings will be based on patient preference and clinical judgment. (15 minutes)

Participants will also be contacted over the course of the take-home phase to ensure compliance and obtain additional insight into device use and effect. Contact will be over phone or email as per their preference. Frequency will be every 2 weeks for the first 3 months and monthly after that until visit 2. Following questions will be asked:

- How many days in the past two weeks/ one month did you use the CROS device?
- On an average, how many hours a day did you use the CROS device?
- In which situations(s) did you find the CROS device most helpful?
- Did you use the noise program?

- Were there any situations where you only listened with the CI processor (with the CROS turned off or muted)?
  - o Why?
- How many days in the past two weeks did you communicate with your FCP in person?

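### Visit 2 repeats only the CROS-On condition, so the change from visit 1 cannot isolate the effect of chronic experience from retest, time and test-order effects

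*Combined protocol and SAP*

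**What the plan says.** All places are in the combined protocol and SAP.

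- **Visit 1, step f**: "Measure benefit in speech understanding with CI only and with CI+CROS in the following listening configurations (50 minutes". Four configurations follow: SpeechFront, SpeechCROS(Off), SpeechCROS(Off)NoiseCI and SpeechCROS(On)NoiseCI. The last two are a matched Off/On pair.
- **Visit 2, step e**: "Measure benefit in speech understanding with CROS device at the same SNR that was used in visit 1". Two items follow: "SCROS(On)NCI (with P1, to assess the effect of chronic experience" and "SFrontNBack (with P1 and with P2, to assess the benefit of UltraZoom".
- **Visit 2, step d** holds the test program constant: "Program 1: Same as that used for speech testing in visit 1".
- **Interval**: no length is stated, but the contact schedule implies more than 3 months: "Frequency will be every 2 weeks for the first 3 months and monthly after that until visit 2".
- **Use of the device** is asked about at these contacts, for example "On an average, how many hours a day did you use the CROS device". No analysis relates the answers to the speech scores.
- **Design** mentions no control group. **Sample Size** gives 15 at Utah and up to 35 in all centers.
- **Purpose and Objectives** states hypotheses on CROS benefit and on quality of life. Chronic experience is not among them.
- **Statistical methods, data analysis, and interpretation** names ANOVA and paired t-tests for speech scores, with no contrast for this comparison. It also names a correlation between speech and questionnaire changes, without saying which speech change is meant.

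**The concern.** Step e gives the repeated CROS-On test a specific purpose: to show what months of CROS use do to speech understanding. The data for that purpose are two CROS-On scores per person, months apart, with nothing to show how far the score would have moved without the experience. A person may score differently at visit 2 because the task and booth are familiar, because of the day or the elapsed time, or because the test falls at a different point in the session. None of these is an effect of CROS experience.

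The stem of step e also speaks of measuring benefit. In this configuration visit 2 has no Off score, so neither the CROS benefit at visit 2 nor its change since visit 1 can be computed. If a rise in the On score were reported under the stated purpose, the study would claim acclimatisation that its design cannot show. If order or session effects pulled the score down, a real gain could be missed.

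**Working it through.** **1. Which conditions link the visits**

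| Condition | Visit 1 | Visit 2 |
|---|---|---|
| Speech front | yes | no |
| Speech at CROS side, Off | yes | no |
| Speech at CROS side, noise at CI, Off | yes | no |
| Speech at CROS side, noise at CI, On | yes (listed last of four) | yes (listed first) |
| Speech front, noise back (P1 and P2) | no | yes |

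Only the On condition appears at both visits. The front/back test is new at visit 2 and gives no retest reference.

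**2. What the available contrast estimates**

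On(visit 2) − On(visit 1) = experience + retest + time/session + order.

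One mean change cannot be split into four unknown parts, whichever test is used. Repeating Off would give

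[On − Off at visit 2] − [On − Off at visit 1] = experience effect on On + (nuisance shift in On − shift in Off).

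The bracket vanishes only if On and Off shift equally.

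**3. Direction**

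Familiarity would raise the visit 2 score. Testing order is not stated. If the listed order is followed, On comes after three other configurations at visit 1 and after none at visit 2, which could lower it. The sign of the net bias is therefore not known.

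**4. Illustration of size**

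The plan has no figure to reproduce: it gives no retest gain, SD, alpha or score scale. Only n = 35 and n = 15 come from the documents. Assumed: true experience effect 0, SD of the change 15 points, two-sided 5% paired t-test. Then

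P(significant rise) = P(T > t₀.₉₇₅), where T is noncentral t with n − 1 df and ncp = (shift/SD)·√n.

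Critical values are 2.032 (n = 35) and 2.145 (n = 15). For a 5-point shift, ncp = (5/15)·√35 = 1.97 and (5/15)·√15 = 1.29.

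| Net shift | SD | n = 35 | n = 15 |
|---|---|---|---|
| 0 | 15 | 2.5% | 2.5% |
| +1 | 15 | 5.7% | 4.3% |
| +5 | 15 | 48% | 22% |
| +2 | 20 | 8.3% | 5.5% |
| +8 | 10 | 99.6% | 82% |

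By symmetry, a net shift of −5 at SD 15 gives a significant fall with probability 48% or 22%.

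**5. The same check on the On-minus-Off contrast**

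SD of the contrast = 15·√(2(1 − ρ)), where ρ is the correlation between the On and Off changes: 21.2 at ρ = 0 and 15 at ρ = 0.5.

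- Equal shifts in On and Off: 2.5% at either n.
- Shifts differing by 2 points (ρ = 0): 7.8% (n = 35), 5.3% (n = 15).
- On gains 5 and Off gains 0 (ρ = 0): ncp = (5/21.2)·√35 = 1.39 and (5/21.2)·√15 = 0.91, giving 27% (n = 35) and 13% (n = 15).

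Standard error: 15/√35 = 2.5 for the On-only change against 21.2/√35 = 3.6 for the contrast at ρ = 0; at n = 15, 3.9 against 5.5. The ratio is √2, about 1.4.

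**The case against.** **Scope.** Chronic experience appears only in one parenthetical and is not a hypothesis, and the statistics section plans no contrast or conclusion for it. This stands and limits the point to one comparison. It does not remove it, because the protocol still states a purpose that the data cannot serve.

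**Controls already present.** SNR and program are fixed, participants have at least 6 months of CI use, and the long interval may weaken memory of test material. These limit settings differences and early post-implant change, but none supplies a retest reference.

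**One-sided illustration.** Assuming a positive gain presupposes the problem. This stands: at zero shift the false-rise rate is nominal, and the listed order could push the change down. The figures show sensitivity, not what will happen in this trial.

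**Weak remedy.** Speech on the non-CI side with noise at the CI is a hard CI-only condition. Off scores may be near floor and show little retest gain, so the contrast would not remove the gain in On. The documents give no score levels, so this is a possibility only. It stands as a reason to treat the Off repeat as preferred but optional.

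**A stronger reading.** A reader might infer that the study's CROS benefit claim is compromised, or that any experience effect will be overstated. The documents support neither. Hypothesis (a) rests on the Off/On comparison within visit 1, and the direction of the bias is not established.

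**Conclusion.** The visit-to-visit change in the CROS-On score does not identify the effect of chronic experience. That follows from the condition lists and the lack of a control group, and needs no assumed figure.

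The size of the bias in this trial is unknown and its direction is open. The 48% and 22% rest on an assumed 5-point gain, SD 15 and no true effect.

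The effect is confined to this comparison. Hypothesis (a), hypothesis (b) on the questionnaires, and the UltraZoom contrast within visit 2 are unaffected. The speech-questionnaire correlation inherits the problem only if its speech change is the visit-to-visit CROS-On change, which the plan does not say.

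The wording should be fixed; adding a test condition is a judgement about visit time and precision.

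**What to change.** **Minimum, at no cost.**
- In visit 2 step e, replace the stated purpose with: *change in CROS-On score from visit 1 to visit 2 (experience plus retest, time and order effects)*.
- Draw no acclimatisation conclusion from it.
- In the statistics section, state which speech change enters the correlation with questionnaire changes. If it is this one, give it the same label.

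**Preferred, if visit time allows.**
- Add SCROS(Off)NCI with P1 at the same SNR at visit 2, with the same order rule for On and Off at both visits.
- Report (On − Off at visit 2) − (On − Off at visit 1) with its 95% CI, beside the On-only change.
- State that it assumes equal retest and time effects with CROS on and off, which may fail if Off is near floor, and that Off may itself change after CROS use.

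**Cost of the preferred fix.**
- *Time*: about 15/3 = 5 minutes by visit 2's own timing. Visit 1's timing suggests up to 50/4 = 12.5, a loose figure because those 50 minutes may cover more than four runs. Visit 2 is already full (30 + 15 + 15 = 60 minutes).
- *Precision*: at SD 15 with uncorrelated On and Off changes, the SE is 1.4 times larger. The effect detectable with 80% power rises from 7.3 to 10.3 points (n = 35) and from 11.7 to 16.5 (n = 15). At correlation 0.5 there is no loss.
- *Residual bias*: if On gains 5 points and Off none, false attribution is still about 27% (n = 35) or 13% (n = 15) at SD 15 with uncorrelated changes.

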
**Procedures performed for research purposes only:**

The quality of life surveys and hearing tests are all for research.

## **Statistical Methods, Data Analysis and Interpretation**

---

### **Statistical methods, data analysis, and interpretation:**

- Questionnaire ratings: Wilcoxon Signed Rank Test
- Speech understanding scores: ANOVA, paired sample t-Tests
- Correlation between changes measured via speech perception scores and questionnaires

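### Quality-of-life ratings are collected only from people who attend visit 2, so the paired analysis may overstate the change if those who benefit least are less likely to return

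*Combined protocol and SAP*

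**What the plan says.** Under Purpose and Objectives, hypothesis (b) is directional: "Use of the CROS device will lead to positive changes in ratings on Quality of Life measures", for CI recipients and for their frequent communication partners (FCPs).

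Baseline questionnaires are mailed out and carried by hand to visit 1 (Procedures, Screening). The only later ratings are in the visit 2 procedures, items a and b: "Obtain post-intervention questionnaire ratings from CI recipients (complete on the same forms that were used for pre-intervention ratings") and "Obtain post-intervention questionnaire ratings from FCPs (complete on the same form that was used for pre-intervention ratings").

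Between visits, "Participants will also be contacted over the course of the take-home phase to ensure compliance". These phone or email contacts are fortnightly for three months and then monthly up to visit 2. They ask the recipient about days and hours of CROS use and about listening with CROS off. Consent tells participants of "their right to withdraw from the study at any time, for any reason".

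The analysis section gives "Questionnaire ratings: Wilcoxon Signed Rank Test" and lists correlations between speech and questionnaire changes. Sample Size gives 15 at Utah and "All Centers: up to 35". The plan gives no analysis set, missing-rating rule, expected dropout, alpha, sidedness or route for collecting ratings outside visit 2.

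**The concern.** A signed-rank test needs both halves of a pair. With visit 2 as the sole source of the second half, the hypothesis (b) analysis is complete-case by construction. The partner's SOS-HEAR is taken at the same visit, so a recipient who does not attend will in practice usually cost the partner's rating too.

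Non-return over several months of home use of a device may well be related to how useful the device was. If the people lost are mainly those with little or negative change, the remaining changes are shifted in the direction that the hypothesis predicts. In a single-group before–after comparison, no control arm offsets that shift. Nor can it be repaired at analysis, because ratings that were never sought cannot be recovered. The choice therefore has to be made in the procedures as well as in the statistics section.

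**Working it through.** The plan states no power, effect size or dropout figure, so there is nothing to reproduce first.

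**Inputs from the documents.** 35 enrolled (the ceiling for all centres) and 15 (Utah), both read as numbers of CI recipients; a signed-rank test on pre–post pairs.

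**Assumptions.** Two-sided 5% test (2.5% in the direction of benefit); standard-normal changes with true mean 0; k people without a visit 2 rating; correlation ρ between a person's change and their tendency to return.

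**Step 1: shift in the mean.** With proportion lost d = k/n and z_d the d-quantile of the standard normal, the large-sample shift in SDs of change is ρ·φ(z_d)/(1 − d).
- 4 of 35: d = 0.114, z_d = −1.204, φ = 0.193. 0.193/0.886 = 0.218; times 0.5 = 0.109.
- 7 of 35: d = 0.20, z_d = −0.842, φ = 0.280. 0.280/0.80 = 0.350; times 0.5 = 0.175.

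Simulation with exactly 4 or 7 people removed (10,000 runs per setting) gives slightly less: +0.10 and +0.17 SD.

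**Step 2: false-benefit rate of the signed-rank test, simulated.**

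| Enrolled | Lost | ρ | Mean shift (SD) | False benefit |
|---|---|---|---|---|
| 35 | 4 / 7 | 0 | 0 / 0 | about 2% / 2% |
| 35 | 4 / 7 | 0.3 | +0.06 / +0.10 | about 5% / 8% |
| 35 | 4 / 7 | 0.5 | +0.10 / +0.17 | about 8% / 15% |
| 35 | 4 / 7 | 1 (exactly the worst changers) | +0.21 / +0.34 | about 22% / 49% |
| 35 | 4 / 7 | −0.5 (good responders lost) | −0.10 / −0.17 | under 1% |
| 15 | 2 / 3 | 0.5 | +0.11 / +0.16 | about 6% / 7% |

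Hand check at ρ = 0.5: the rate is roughly 1 − Φ(1.96 − b√m), with shift b and m pairs left.
- 31 pairs: 0.103 × √31 = 0.573; 1 − Φ(1.387) = 0.083.
- 28 pairs: 0.169 × √28 = 0.894; 1 − Φ(1.066) = 0.143.

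Both agree with the simulation.

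**Step 3: scale.** With 80% power and Wilcoxon efficiency 3/π, 35 complete pairs detect (1.96 + 0.84)/√(35 × 3/π) ≈ 0.48 SD. A shift of 0.17 SD is about a third of that (0.17/0.48 = 0.35).

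**Step 4: what is exposed.** The questionnaire tests, the visit 1 to visit 2 speech comparison, the pre–post data logging and the change correlations all need visit 2. The CI-only versus CI+CROS speech comparison is made within visit 1 (item f) and does not.

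**The case against.** A reader might infer that people who give up on CROS leave the analysis and that the result is therefore biased upwards. The documents do not say this. Nothing withdraws non-users or excuses them from visit 2. Willingness to use the device regularly is an entry criterion, not a discontinuation rule, and a non-user who attends is rated and analysed like anyone else.

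The direction of bias is also not settled. Satisfied users have a reason to attend, because the decision to keep the device is made at visit 2. Dissatisfied users have one too, because their own processor was reprogrammed at visit 1 and its settings are revisited at visit 2. Regular contact and the willingness-to-follow-up criterion both work against loss. The 22% and 49% rates require that exactly the worst changers vanish, so they are an upper bound and not an expectation.

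All of that stands, and it makes the claim conditional. It does not close the gap: returners are still the only people who can be analysed, no dropout figure reassures the reader, and the plan has no route to the missing ratings.

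**Conclusion.** The concern holds in conditional form. By design the hypothesis (b) tests and the change correlations use only those who return, and the quality-of-life change may be overstated if return is related to benefit. Under moderate dependence (ρ = 0.5) with 35 enrolled, the false-benefit rate rises from a nominal 2.5% to about 8% with 4 lost or 15% with 7 lost; with 15 enrolled and 2 or 3 lost, it is about 6% or 7%. The number lost, the correlation, the test level and its sidedness are all assumptions. The bias is nil if return is unrelated to change and reverses if good responders are lost. The point does not extend to the trial's pre–post evidence as a whole: the main speech comparison, within visit 1, is untouched.

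**What to change.** **Visit 2 procedures.** State that, when visit 2 is due, the questionnaires are sought from every CI recipient fitted with CROS at visit 1 and from that recipient's FCP, whether or not CROS is still used and whether or not they attend, unless consent is withdrawn. For non-attenders, send the form by mail or email with a stated way to return it. A return route has to be added, because the baseline forms are mailed out but carried back by hand. If post ratings are to stay on the same form, send a copy of the completed baseline form. Address the FCP as well as the recipient, since the planned contacts are worded for the recipient only.

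**Statistical methods.** Make all such pairs the analysis set for hypothesis (b), and report the number of missing ratings and the reasons beside each result. Add one sensitivity signed-rank analysis that gives the worst rank to those still missing after reporting non-use at the contacts. Label it a conservative bound: when the worst 10% or 20% are lost and ranked this way, simulated false benefit is 0.5% or less, so failing that analysis is not evidence against a benefit.

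**Cost.** A few mailings, some ratings collected by a different route from the rest, one extra analysis, and a possibly less favourable estimate. Use and non-use are already recorded at the contacts, so the sensitivity analysis needs no new data.
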